#### 14.3.8.1 Primary estimand

The primary estimand will use a *hypothetical strategy* which attempts to quantify the effect of treatment, in the hypothetical situation, where one or more intercurrent events do not occur. In this context, an intercurrent event refers to a post-randomisation event that either precludes the existence of or affects the interpretation of the measurements of the endpoint e.g., permanent discontinuation of IMP.

This primary estimand evaluates the treatment difference in change in EASI score from baseline to Week 16 as if all subjects adhered to the treatment regimen, i.e., they did not discontinue IMP permanently and no rescue treatment was made available before Week 16. Data collected after permanent discontinuation of IMP or after initiation of rescue treatment will not be included in the analysis, but will be 'treated as missing' and imputed assuming

THIS DOCUMENT CONTAINS CONFIDENTIAL INFORMATION AND MUST NOT BE COPIED OR MADE AVAILABLE TO ANY THIRD PARTY WITHOUT THE PRIOR WRITTEN CONSENT OF THE LEO PHARMA GROUP

MAR. Similarly, for subjects who experience a pandemic-related intercurrent event prior to Week 16, observed data at Week 16 will be ‘treated as missing’ and imputed assuming MAR.

If data is missing at Week 16 due to a non-pandemic-related intercurrent event, the data will be imputed using MI (100 iterations) assuming MAR within each treatment group and whether the subject has experienced a non-pandemic-related intercurrent event. Within a given treatment group, observed data from subjects not experiencing an intercurrent event will be used to impute missing data for subjects who experience an intercurrent event.

Missing data or data ‘treated as missing’ at Week 16 due to the pandemic will be imputed using MI assuming MAR within treatment group using data from subjects who have not experienced an intercurrent event.

For each of the 100 complete datasets, the change in EASI score from baseline to Week 16 will be analysed using an ANCOVA model adjusted for treatment, region, baseline EASI score, and baseline disease severity. The pooled estimate of the difference in the LS-mean change from baseline, along with the associated 95% CIs and nominal p-values will be presented based on applying Rubin’s rules to the estimates and standard errors from the ANCOVA analysis of the imputed datasets.

#### **14.3.8.1.1 Sensitivity analysis for primary estimand**

The primary estimand will be analysed using a MMRM on the post-baseline responses up to Week 16 including treatment, visit, interaction between treatment and visit, region and baseline disease severity as factors and adjusting for baseline EASI score as covariate. The model will use an unstructured covariance matrix, Kenward-Roger approximation to estimate denominator degrees of freedom. This model assumes that data is missing at random within each treatment group and the model will be used to predict missing data. The estimates will be presented with nominal p-values and 95% CI at each visit.

#### **14.3.8.2 First supplementary estimand**

A first supplementary estimand will use *composite strategy* to handle intercurrent events. A composite strategy accounts for the occurrence of intercurrent events, through the definition of a suitable composite endpoint, whose components include the aforementioned intercurrent events, as well as the endpoint of interest.

The first supplementary estimand for the primary endpoint is the treatment difference in change in EASI score from baseline to Week 16 as if initiation of rescue treatment or permanent discontinuation of IMP did not happen. For subjects who received rescue treatment

THIS DOCUMENT CONTAINS CONFIDENTIAL INFORMATION AND MUST NOT BE COPIED OR MADE AVAILABLE TO ANY THIRD PARTY WITHOUT THE PRIOR WRITTEN CONSENT OF THE LEO PHARMA GROUP

or who have permanently discontinued IMP prior to the endpoint of interest, observed data after the intercurrent events will be considered non-response by using LOCF. Similarly, missing data for subjects who do not attend the visit for the endpoint of interest and do not experience an intercurrent event prior to this visit will be imputed as LOCF.

The change in EASI score from baseline to Week 16 will be analysed using an ANCOVA model adjusted for treatment, region, baseline EASI score, and baseline disease severity. The difference in the LS-mean change from baseline between the treatment groups will be presented along with the corresponding 95% CI and nominal p-value.

#### **14.3.8.2.1 Sensitivity analysis for the first supplementary estimand**

For subjects who received rescue treatment or who have permanently discontinued IMP prior to the endpoint of interest, observed data after the intercurrent events will be considered non-response by using WOCF including the baseline value. Similarly, missing data for subjects who do not attend the visit for the endpoint of interest and do not experience an intercurrent event prior to this visit will be imputed as WOCF. The same ANCOVA model described for the primary analysis of the primary estimand will be used.

#### **14.3.8.3 Second supplementary estimand**

A second supplementary estimand will use a *pandemic-modified composite strategy*. The strategy follows a composite strategy for intercurrent events independent of the COVID-19 pandemic.

The second supplementary estimand for the primary endpoint is the treatment difference in change in EASI score from baseline to Week 16 without initiation of rescue treatment or permanent discontinuation of IMP and as if the COVID-19 pandemic did not happen. For subjects who experience non pandemic-related intercurrent events prior to the endpoint of interest, observed data after the intercurrent events will be considered non-response by using LOCF. For subjects who experience a pandemic-related intercurrent event prior to the endpoint of interest, observed data after the event will be ‘treated as missing’ and imputed assuming MAR.

For imputation purposes, data available from all subjects will be used, but excluding individual subject data captured after the intercurrent events.

The procedure for imputing values will be implemented in a 2-step procedure, where all missing or ‘treated as missing’ data related to pandemic will be imputed using MI (100 iterations) assuming MAR within treatment groups. Once the 100 complete data sets have

THIS DOCUMENT CONTAINS CONFIDENTIAL INFORMATION AND MUST NOT BE COPIED OR MADE AVAILABLE TO ANY THIRD PARTY WITHOUT THE PRIOR WRITTEN CONSENT OF THE LEO PHARMA GROUP

been generated by MI, LOCF imputation of relevant data points not affected by the pandemic will be applied according to the rules described above.

For each of the 100 complete datasets, the change in EASI score from baseline to Week 16 will be analysed using an ANCOVA model including treatment, region, and baseline disease severity as factors and adjusting for baseline EASI score as covariate. The pooled estimate of the difference in the LS-mean change from baseline, along with the associated 95% CIs and nominal p-values will be presented based on applying Rubin's rules to the estimates and standard errors from the aforementioned ANCOVA analysis of the imputed datasets.

#### 14.3.8.4 Third supplementary estimand

A third supplementary estimand will use a *treatment policy strategy* which attempts to quantify the effect of the decision to treat subjects with the randomised treatment, thus ignoring the occurrence of intercurrent events. Data collected for the primary endpoint are used regardless of whether an intercurrent event (independent of the pandemic) occurred. Data collected after an event related to the pandemic will be 'treated as missing' and imputed assuming MAR.

This supplementary estimand will evaluate the treatment difference in change in EASI score from baseline to Week 16 regardless of permanent discontinuation of IMP or initiation of rescue treatment and as if the COVID-19 pandemic did not happen. Observed data will be used in the analysis, including the data observed after the occurrence of non-pandemic-related intercurrent events. For subjects who experience a pandemic-related intercurrent event prior to Week 16, observed data at Week 16 will be 'treated as missing' and imputed assuming MAR.

If data is missing at Week 16 due to a non-pandemic-related intercurrent event, the data will be imputed using MI (100 iterations) assuming MAR within each treatment group and whether the subject has experienced a non-pandemic-related intercurrent event. Within a given treatment group, observed data from subjects not experiencing an intercurrent event will be used to impute missing data for subjects who experience an intercurrent event.

Missing data or data 'treated as missing' at Week 16 due to the pandemic will be imputed using MI assuming MAR within treatment group using data from subjects who have not experienced an intercurrent event.

For each of the 100 complete datasets, the change in EASI score from baseline to Week 16 will be analysed using an ANCOVA model adjusted for treatment, region, baseline EASI

THIS DOCUMENT CONTAINS CONFIDENTIAL INFORMATION AND MUST NOT BE COPIED OR MADE AVAILABLE TO ANY THIRD PARTY WITHOUT THE PRIOR WRITTEN CONSENT OF THE LEO PHARMA GROUP

score, and baseline disease severity. The pooled estimate of the difference in the LS-mean change from baseline, along with the associated 95% CIs and nominal p-values will be presented based on applying Rubin's rules to the estimates and standard errors from the ANCOVA analysis of the imputed datasets.

[Panel 13](#) presents an overview of how observed and missing data will be handled according to the intercurrent events for the analyses of estimands.

THIS DOCUMENT CONTAINS CONFIDENTIAL INFORMATION AND MUST NOT BE COPIED OR MADE AVAILABLE TO ANY THIRD PARTY WITHOUT THE PRIOR WRITTEN CONSENT OF THE LEO PHARMA GROUP

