	
A primary and 3 supplementary estimands will be defined for the primary endpoint to ensure that occurrence of intercurrent events is taken into account.
 
 
• The primary estimand for the primary endpoint will use a hypothetical strategy which attempts to quantify the effect of treatment, in the hypothetical situation, where one or more intercurrent events do not occur.
 
• A first supplementary estimand will use a composite strategy which accounts for occurrence of pre-defined intercurrent events (initiation of rescue treatment and permanent discontinuation of IMP) as a component of the endpoint.
 
• A second supplementary estimand will use a pandemic-modified composite strategy which follows a composite strategy for intercurrent events independent of the COVID-19 pandemic, attempting to quantify the effect of the randomised treatment as if the COVID-19 pandemic did not happen.
 
• A third supplementary estimand will use a treatment policy strategy which attempts to quantify the effect of the randomised treatment regardless of whether an intercurrent event occurs.
 
 
For the primary analysis of the primary estimand, missing data at Week 16 due to an intercurrent event will be imputed using MI (100 iterations) assuming MAR within each treatment group and whether the subject has experienced an intercurrent event. Within a given treatment group, observed data from subjects not experiencing an intercurrent event will be used to impute missing data for subjects who experience an intercurrent event.
 
For each of the 100 complete datasets after imputation, the change in EASI score from baseline to Week 16 will be analysed using an ANCOVA model adjusted for treatment, region, baseline EASI score, and baseline disease severity. The pooled estimate of the difference in the LS-mean change from baseline, along with the associated 95% CIs and nominal p-values will be presented based on applying Rubin's rules to the estimates and standard errors from the ANCOVA analysis of the imputed datasets.
 
The 3 supplementary estimands will be analysed using the same ANCOVA model with different imputation methods for intercurrent events.
 
The secondary endpoint (number of treatment-emergent AEs from baseline to Week 16 per subject) will be reported descriptively by treatment group.

Signatory investigator	    Germany

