### Panel 13: Handling of intercurrent events and analyses of estimands for the primary endpoint

Events	Data observed or missing	Estimand strategy			
		Primary: 'Hypothetical'	First supplementary: 'Composite'	Second supplementary: 'Pandemic modified composite'	Third supplementary: 'Treatment policy'
Initiation of rescue treatment a	Observed	MI (MAR)	LOCF	LOCF	Used
	Missing	MI (MAR)	LOCF	LOCF	MI (MAR)
Permanent discontinuation of IMP independent of the pandemic	Observed	MI (MAR)	LOCF	LOCF	Used
	Missing	MI (MAR)	LOCF	LOCF	MI (MAR)
Permanent discontinuation of IMP related to the pandemic	Observed	Treated as missing, MI (MAR)	LOCF	Treated as missing, MI (MAR)	Treated as missing, MI (MAR)
	Missing	MI (MAR)	LOCF	MI (MAR)	MI (MAR)
No intercurrent events	Observed	Used	Used	Used	Used
	Missing independent of the pandemic	MI (MAR)	LOCF	LOCF	MI (MAR)
	Missing related to the pandemic	MI (MAR)	LOCF	MI (MAR)	MI (MAR)

**Abbreviations:** COVID-19 = coronavirus disease 2019; IMP = investigational medicinal product; LOCF= last observation carried forward;

MAR = missing at random; MI = multiple imputation.

a Initiation of rescue treatment is considered an intercurrent event regardless of the relatedness to the COVID-19 pandemic.

THIS DOCUMENT CONTAINS CONFIDENTIAL INFORMATION AND MUST NOT BE COPIED OR MADE AVAILABLE TO ANY THIRD PARTY WITHOUT THE PRIOR WRITTEN CONSENT OF THE LEO PHARMA GROUP

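### The treatment-policy estimand (14.3.8.4) imputes Week 16 EASI missing after discontinuation or rescue from event-free subjects, which does not fit its target

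*Combined protocol and SAP*

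**What the plan says.** Section 14.3.8.4 defines the third supplementary estimand as the difference in EASI change to Week 16 "regardless of permanent discontinuation of IMP or initiation of rescue treatment", with the pandemic hypothetically removed. Observed values enter the analysis, "including the data observed after the occurrence of non-pandemic-related intercurrent events".

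Two consecutive sentences cover Week 16 EASI that is missing because of a non-pandemic event. The first prescribes multiple imputation "assuming MAR within each treatment group and whether the subject has experienced a non-pandemic-related intercurrent event". The second names the donors: within an arm, "observed data from subjects not experiencing an intercurrent event will be used to impute missing data for subjects who experience an intercurrent event".

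Both sentences also stand, in the same words, in Section 14.3.8.1 for the hypothetical primary estimand. There the post-event data are discarded: "Data collected after permanent discontinuation of IMP or after initiation of rescue treatment will not be included in the analysis".

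Panel 13 ("Handling of intercurrent events and analyses of estimands for the primary endpoint") shows, in the treatment-policy column, that values observed after rescue or non-pandemic discontinuation are used and that missing ones get MI under MAR. It names no donors.

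**The concern.** An event-free donor is a subject still on IMP and not using rescue. Drawing from such donors answers the question of what the value would have been without the event. That is the primary estimand's question, not this one's.

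A subject who stops IMP and attends Week 16 contributes the post-discontinuation value (treatment policy). A subject with the same history who misses Week 16 contributes an on-treatment value (hypothetical). The estimate then mixes two strategies according to attendance. The first sentence, which conditions on event status, points to donors who did have an event, so it does not support the donor sentence either.

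At stake is the one estimand intended to describe the effect of assigning treatment whatever non-pandemic events follow.

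**Working it through.** **Can the affected subjects and suitable donors both occur?** Yes. Under Section 10.1 a subject who withdraws stops IMP and all trial activities, so event subjects can miss Week 16. Under Section 9.5 subjects rescued after Week 4 stay on IMP and on the visit schedule, and under Section 10.3 subjects who discontinue IMP are asked to attend Week 16. Post-event values can therefore be observed.

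**Where does the donor sentence fit?** In 14.3.8.1 all post-event values are set to missing. Event-free donors are the only possible ones there, and they match the target. In 14.3.8.4 post-event values are kept and neither statement holds.

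**The plan's own figures.** The plan gives no figure for the donor rule. Its sample size (14.1) reproduces: difference 22.9 − 7.3 = 15.6, SDs 13 and 18, 18 per arm, t-test power 0.825; 18/0.70 = 25.7, rounded up to 26. The donor rule does not enter this calculation.

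**Illustrative size.** Let p be the share of an arm with a non-pandemic event, m the share of those who miss Week 16, q = p × m, and x the mean EASI reduction of event subjects (A = LEO 138559, P = placebo). Assume that 22.9 and 7.3 are the event-free means, and that observed and missing event subjects share the mean x. The plan states neither.

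- Target: T = (1 − pA) × 22.9 + pA × xA − (1 − pP) × 7.3 − pP × xP
- Shift caused by event-free donors: qA × (22.9 − xA) − qP × (7.3 − xP)
- Hypothetical difference: H = 15.6

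With p = 0.30 and m = 0.5 in both arms (q = 0.15):

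| xA / xP | T | Shift |
|---|---|---|
| 7.3 / 7.3 | 10.92 | 0.15 × 15.6 = +2.34 |
| 18 / 7.3 | 14.13 | 0.15 × 4.9 = +0.74 |
| 18 / 2.4 | 15.60 | 0.15 × (4.9 − 4.9) = 0 |
| 18 / 0 | 16.32 | 0.15 × (4.9 − 7.3) = −0.36 |

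If instead 30% of each arm both had an event and missed Week 16 (q = 0.30), the shifts double to +4.68, +1.47, 0 and −0.72.

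When m is equal in the arms, shift = m × (H − T), a move toward the hypothetical value. With unequal m this is not guaranteed. Take x = 12 / 0, so T = 16.03 + 3.6 − 5.11 = 14.52:

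- m = 0.25 (A), 0.75 (P): 0.075 × 10.9 − 0.225 × 7.3 = −0.83, giving 13.70, away from 15.6.
- m = 0.75 (A), 0.25 (P): 0.225 × 10.9 − 0.075 × 7.3 = +1.91, giving 16.43, past 15.6.

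For scale, the standard error of the difference at 26 per arm is √(13²/26 + 18²/26) = 4.35.

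**How many event donors?** With p = 0.30 and m = 0.5, observed event donors per arm follow Binomial(26, 0.15), mean 3.9. P(2 or fewer) = 0.015 + 0.067 + 0.148 = 0.23 per arm, and 1 − 0.77² = 0.41 for at least one arm. With m = 0.75 it is 0.69 per arm.

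**The case against.** Several points on the other side stand.

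- A reader might infer that 14.3.8.4 gives two executable donor rules, so that two analysts would get different results. The text does not go that far. Only the second sentence names donors, and the event-status clause can be read as marking who is imputed. That leaves one explicit rule, and it is this rule that misses the target.
- A reader might infer a conflict with the synopsis, which says "The 3 supplementary estimands will be analysed using the same ANCOVA model with different imputation methods for intercurrent events". Panel 13 shows that the methods do differ: observed post-event values are used here and imputed under the primary.
- A reader might take the estimand as pure treatment policy. It is already hypothetical for pandemic-related events, so the mismatch concerns non-pandemic events only.
- A reader might infer a known bias toward the hypothetical result. Every event rate, event mean and missing share above is an assumption, and the sign can go either way.
- Using event donors alone is no clean remedy. They may be too few for a regression on baseline, and they pool rescued subjects still on IMP with subjects who stopped it, although withdrawals are a likely source of the missing values.

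These points limit the claim and shape the remedy. They do not make event-free donors suitable for a target that disregards non-pandemic events, and nothing else in the combined document repairs the sentence.

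**Conclusion.** The point holds in a limited form. The explicit donor sentence in 14.3.8.4 assigns on-treatment, rescue-free values to subjects who stopped IMP or used rescue and then missed Week 16. This does not fit the stated target and mixes strategies by attendance.

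Size and sign cannot be derived from the documents. The half-missing illustrations with equal missing shares lie well within one standard error; the largest figure, +4.68, slightly exceeds it, but needs 30% of each arm to have an event with Week 16 missing and LEO event subjects to fall to the placebo mean.

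Only the third supplementary estimand is affected, and all p-values are nominal (14.3.7). The primary analysis, sample size and power are unchanged. The sentence should be corrected before the code is broken, but it gives no reason to doubt the primary result.

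**What to change.** In 14.3.8.4, replace the event-free donor sentence. Week 16 values missing after a non-pandemic event should be imputed from same-arm observed Week 16 data, including data observed after such events, with event status in the imputation model. Where numbers allow, separate IMP discontinuation from rescue while on IMP.

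In the SAP, which Section 14.3.1 says is finalised before the randomisation code is broken, pre-specify a minimum donor count and one named fallback for an arm with too few event donors. An event-status effect estimated jointly across arms is one example. Report donor counts per arm.

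As a tidy-up only, delete the event-status clause in 14.3.8.1 and its counterpart in the synopsis ("assuming MAR within each treatment group and whether the subject has experienced an intercurrent event"). It cannot operate there, because event-free donors are the only possible ones.

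The cost is wording plus one SAP rule. The downside is few donors, a wider interval and some reliance on the fallback for this one estimand.

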### Panel 13: Handling of intercurrent events and analyses of estimands for the primary endpoint

Events	Data observed or missing	Estimand strategy			
		Primary: 'Hypothetical'	First supplementary: 'Composite'	Second supplementary: 'Pandemic modified composite'	Third supplementary: 'Treatment policy'
Initiation of rescue treatment a	Observed	MI (MAR)	LOCF	LOCF	Used
	Missing	MI (MAR)	LOCF	LOCF	MI (MAR)
Permanent discontinuation of IMP independent of the pandemic	Observed	MI (MAR)	LOCF	LOCF	Used
	Missing	MI (MAR)	LOCF	LOCF	MI (MAR)
Permanent discontinuation of IMP related to the pandemic	Observed	Treated as missing, MI (MAR)	LOCF	Treated as missing, MI (MAR)	Treated as missing, MI (MAR)
	Missing	MI (MAR)	LOCF	MI (MAR)	MI (MAR)
No intercurrent events	Observed	Used	Used	Used	Used
	Missing independent of the pandemic	MI (MAR)	LOCF	LOCF	MI (MAR)
	Missing related to the pandemic	MI (MAR)	LOCF	MI (MAR)	MI (MAR)

**Abbreviations:** COVID-19 = coronavirus disease 2019; IMP = investigational medicinal product; LOCF= last observation carried forward;

MAR = missing at random; MI = multiple imputation.

a Initiation of rescue treatment is considered an intercurrent event regardless of the relatedness to the COVID-19 pandemic.

THIS DOCUMENT CONTAINS CONFIDENTIAL INFORMATION AND MUST NOT BE COPIED OR MADE AVAILABLE TO ANY THIRD PARTY WITHOUT THE PRIOR WRITTEN CONSENT OF THE LEO PHARMA GROUP

### 14.3.9 Analysis of secondary endpoint

Analysis of the secondary endpoint

- Number of treatment-emergent adverse events from baseline to Week 16 per subject. is described in Section [14.3.14.1](#) in details.

### 14.3.10 Analysis of exploratory efficacy endpoints

#### Binary endpoints

The following endpoints;

- Having a decrease in EASI of at least 50% (EASI 50) from baseline to Week 16.
- Having a decrease in EASI of at least 75% (EASI 75) from baseline to Week 16.
- Having a decrease in EASI of at least 90% (EASI 90) from baseline to Week 16.
- Having vIGA-AD of 0 (clear) or 1 (almost clear) at Week 16.

will be analysed using CMH test stratified by region and baseline disease severity. Subjects who received rescue treatment prior to the Week 16 visit or permanently discontinued IMP or have missing data will be considered as non-responders. Additionally, responder rates will be summarised descriptively at each visit by treatment group.

